6. DATA AND SAFETY MONITORING

6.1 DATA SAFETY MONITORING BOARD

A Data and Safety Monitoring Board (DSMB) will be appointed to review TO 005 PACT and to provide recommendations about trial continuation to the IDE Sponsor. After initial approval and at periodic intervals (to be determined by the committee) during the trial, the DSMB responsibilities are to:

- a. Review the research protocol, informed consent documents, and plans for data and safety monitoring.
- b. Evaluate the progress of the trial, including periodic assessments of data quality and timeliness, subject enrollment and retention, subject risk versus benefit, adverse events, unanticipated problems, performance of the trial sites, and other factors that can affect the trial outcome.
- c. Consider relevant external information, such as scientific or therapeutic developments that may have an impact on the safety of the subjects or the ethics of the trial.
- d. Review clinical center performance, make recommendations, and assist in the resolution of problems reported by the IDE Sponsor or site investigators.
- e. Protect the safety of the trial subjects.
- f. Report on the safety and progress of the trial.
- g. Make recommendations to the IDE Sponsor and, if required, to the FDA concerning continuation, termination, or other modifications of the trial based on the observed beneficial or adverse effects of the intervention.
- h. Monitor the confidentiality of the trial data and the results of site monitoring
- i. Assist the IDE Sponsor by commenting on any problems with conduct of the trial, enrollment, sample size, and/or data collection.

The DSMB will include experts in emergency medicine, surgery (trauma / critical medicine), bioethics, and biostatistics. DSMB members must be independent of the investigators and have no financial, scientific, or other conflict of interest with the trial. Written documentation attesting to the absence of conflict of interest will be required.

The University of Pittsburgh Office of Clinical Research, Health Sciences will provide logistical management and support for the DSMB. A safety officer (chairperson) will be identified at the first meeting. This person will be the contact person for serious adverse event reporting. Procedures for this will be discussed at the first meeting.

The first DSMB meeting will take place before trial initiation to discuss the protocol, approve the commencement of the trial, and establish guidelines to monitor the trial. The frequency of further meetings will be determined during the first meeting. An emergency meeting of the DSMB will be called at any time by the chairperson should questions of subject safety arise.

6.2 DATA SAFETY MONITORING PLAN

Monitoring of safety and data quality in the proposed study will be the responsibility of all personnel on the project, with primary responsibility and supervision by the Investigator. The Institutional Review Board will approve the Statement of Informed Consent for the study and provide institutional oversight of data and safety issues. The study protocol will be approved prior to enrolling any participants. Moreover, the study will be reviewed at a minimum of annual basis (or more frequently as deemed necessary) by the IRB committee. Regarding monitoring of data quality and protected health information, all required personnel proposed for this project will have the required human subjects and confidentiality training, which includes information about maintaining data integrity and security. Confidentiality will be guarded using established procedures such as storing source documents containing patient identifiers in locked cabinets within locked offices or locked data rooms, using study IDs rather than subject identifiers in the electronic data management system, and aggregating data across subjects. The key linking subject names and study identification numbers will be kept separately from the data sets with limited access by study personnel. Only study personnel will have access to the data sets on protected servers. Oversight of all aspects of data management will occur with the DCC.

6.2.1 Parameters to be Monitored

The following parameters will be monitored by the DSMB throughout the course of the research to ensure the safety of subjects as well as the integrity and confidentiality of their data.

- An evaluation of the progress of the research study, including subject enrollment and retention as well as an assessment of the timeliness and quality of the data.
- A review of collected data (including adverse events, unanticipated problems, and subject withdrawals) to determine whether there is a change to the anticipated benefit-to-risk assessment of study participation and whether the study should continue as originally designed, should be changed, or should be terminated.
- A review of study procedures designed to protect the privacy of the research subjects and the confidentiality of their research data.

6.2.2 Frequency of Monitoring

The Investigator, sub-investigators, and the research staff will meet regularly to re-evaluate study goals, subject recruitment, data coding and retention, documentation and identification of adverse events, complaints and confidentiality of subjects. There will be an evaluation of the progress of the research study, including assessments of data quality, time lines, participant recruitment, accrual, and retention. The Investigator will also review the outcome and adverse event data to determine whether there is any change to the anticipated benefit-to-risk ratio of study

participation and whether the study should continue as originally designed or should it be re-evaluated and changed.

6.3 REPORTABLE ADVERSE EVENTS

An adverse event (AE) refers to any untoward medical occurrence caused by, or associated with, the study or study device(s). All potential AEs will be documented by the sites using the electronic data management system. All reported adverse events will be reviewed in consideration of the treatment arm and further classified by a) Severity (serious or non-serious); and b) Expected or Unexpected. For serious, unexpected adverse events felt to be possibly associated with the research intervention, the Coordinating Center will notify the reviewing IRB, FDA, DSMB, and Department of Defense in accordance with requisite reporting time frames.

Some adverse events are commonly observed in patients following traumatic injury and may or may not be attributable to the airway management. Examples of these include Fat Embolism Syndrome, cardiac arrest, myocardial infarction, sepsis, cerebral bleeding, stroke, Deep Vein Thrombosis (DVT), pulmonary embolus, rhabdomyolysis, abdominal compartment syndrome, upper gastrointestinal bleeds, HITT, extremity compartment syndrome, seizures, surgical interventions, complications due to specific injuries as well as other major medical or surgical complications are commonly observed in these patients.

Some of these events may be recorded as noted in the medical record however, none of the expected events will be reported as adverse events.

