2.5 STUDY ENDPOINTS

Primary Outcome: The primary outcome for the trial is 24-hour survival.

Secondary Outcomes: Secondary outcomes include survival to hospital discharge, expected clinical events (including incorrect placement of the airway, inadequate ventilation, airway trauma, or concern for aspiration as defined as documented vomiting and/or need for suctioning), airway management performance (including initial pass success, overall success, and use of rescue technique), ICU length of stay, ventilator days, and expected adverse events including airway trauma, pneumothorax, incidence of acute respiratory distress syndrome (ARDS) and incidence of ventilator associated pneumonia (VAP).

Primary Outcome Definition:

24-hour Mortality: A binary variable defined as death within 24 hours

Secondary Outcome Definitions:

Secondary outcomes will be assessed from arrival at the trauma center through day 30 or discharge, whichever is first.

In-Hospital Mortality: A binary variable defined as death recorded any time after hospital arrival.

Airway Management Performance: The elements of airway management performance include airway misplacement (including endotracheal tube misplacement), initial pass success (the successful placement of device on the first attempt past the teeth confirmed by EtCO₂), sequence of airway insertion, airway insertion success and time, number of airway insertion attempts, inadequate ventilation, and any instances of airway conversion (change of airway in the first 24 hours).

Acute Respiratory Distress Syndrome (ARDS): The Berlin definition for mild ARDS ($\text{PaO}_2/\text{FIO}_2 \leq 300$ mm Hg plus timing, imaging, and origin criteria) will be utilized as a threshold value to determine the incidence of ARDS within 24 hours of presentation. We will further stratify patients into mild, moderate ($\text{PaO}_2/\text{FIO}_2 \leq 200$ mm Hg), or severe ($\text{PaO}_2/\text{FIO}_2 \leq 100$ mm Hg) ARDS.¹⁶

ICU length of stay (LOS): Defined as the number of days spent admitted to the Intensive Care Unit. ICU LOS will be recorded to the first decimal place.

Ventilator Days: Defined as number of days on a mechanical ventilator. Ventilator days will be recorded to the first decimal place.

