2.6.6 Interim Analyses

Prior to initiation, and in concert with the DSMB, the final monitoring plan will be developed to serve as a guide to the DSMB's decision-making process concerning early stopping of the trial. In making the decision to recommend termination of the trial, the DSMB will be guided by information on safety outcomes by treatment group.

Two interim safety analyses will be conducted, one at the completion of the second step (third period) and one at the completion of the fourth step (fifth period, out of seven periods). The frequency of the composite safety outcome (mortality, failure to place an advanced airway on first attempt, failure to

ventilate) in the two groups will be summarized. The null hypothesis that there is no difference in the proportion of the rate of the composite safety outcome between the two groups will be tested using a generalized linear mixed model. Group sequential methods, such as a Lan and Demets approach with an O'Brien and Fleming spending function will be used to ensure that the overall type I error rate of 0.05 is maintained across the three tests (two interim and one final), with the majority of the type I error reserved for the final test. Based on the expected recruitment of 287 participants per period (2,009/7 periods), we expect a sample size of 861 for the first interim analysis (information fraction of 43%) and 1,435 for the second interim analysis (information fraction of 71%). For the first interim analysis the upper/lower boundaries will be ± 3.22 with a nominal alpha level of 0.001. The second interim analysis will have upper/lower boundaries of ± 2.42 with a nominal alpha level of 0.015. The final analysis will have upper/lower boundaries of ± 2.00 with a nominal alpha level of 0.045.

Further—and in relation to the interim safety analyses—safety data by group will be provided periodically to the DSMB. Safety data serious adverse events include frequency, a description of each event, and the date of each event.

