6.3.1 Adverse Events Reporting Timeline

A table summarizing reporting timelines is provided below:

Organization	Fatal/Life Threatening Reportable Adverse Event	Non-fatal, non-life threatening Reportable Adverse Event	Expected Adverse Events	Unanticipated Problem (not involving risk)	Unanticipated Problem (involving risk)
IRB	24 hours	10 working days	No requirement	No requirement	10 working days
FDA	7 calendar days	15 calendar days	No requirement	No requirement	14 days*
Dept of Defense	7 calendar days	No requirement	No requirement	No requirement	14 days*
DSMB	24 hours	7 calendar days	No reporting	At next meeting (every 6 months)	14 days*

*Reporting occurs only after an IRB determination of UPIRTSO has been received

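### Section 6.3 exempts cardiac arrest and an open-ended class of complications from adverse event reporting, with no limit on onset or attribution, so a non-fatal arrest around airway insertion need not be reported individually

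*Combined protocol and SAP*

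**What the plan says.** Section 6.3 describes events often seen after injury that "may or may not be attributable to the airway management". The list begins "Examples of these include Fat Embolism Syndrome, cardiac arrest, myocardial infarction, sepsis" and ends with "complications due to specific injuries as well as other major medical or surgical complications are commonly observed in these patients". The section then says that some of these may be recorded, but that "none of the expected events will be reported as adverse events".

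Earlier in the same section, sites are to document all potential adverse events in the data system. Reported events are reviewed with the arm in mind and classed by seriousness and expectedness. Notice to the IRB, FDA, DSMB and Department of Defense is triggered by events that are serious, unexpected and possibly related to the intervention.

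The table in 6.3.1 has a column headed "Expected Adverse Events". Under it, the IRB, FDA and Department of Defense rows carry no requirement, and the DSMB row says these events are not reported.

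Two other places bear on this. Section 2.6.6 promises the DSMB periodic safety data by group: "Safety data serious adverse events include frequency, a description of each event, and the date of each event". Section 2.5 lists, among the secondary outcomes, "expected adverse events including airway trauma, pneumothorax, incidence of acute respiratory distress syndrome" and ventilator-associated pneumonia. Cardiac arrest is not on that list.

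**The concern.** Section 3.3 excludes patients in cardiac arrest without return of circulation at the time of the intervention. An enrolled patient should therefore have a pulse when the airway is attempted, and an arrest during or just after the attempt is a new event under the assigned strategy. It is among the acute harms one would most want compared between arms.

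The exemption does not separate such an arrest from one caused hours later by the injuries. The catch-all at the end of the list also allows almost any serious complication to be called expected, which leaves the expedited route little to carry. The trial enrolls under an exception from informed consent, for which the protocol cites independent data monitoring as a required protection. If the rule is followed as written, an excess of non-fatal arrests in one arm could stay out of the DSMB's view.

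**Working it through.** No figure in the plan settles the point, so the check sets the sections side by side. Exposure arithmetic follows.

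**1. Is arrest in the exempt class?** Section 6.3 does not say outright that every listed event is expected. The exempting sentence follows the list directly and opens by referring back to it, so the natural reading is that the listed events are the expected ones. Section 2.5 uses the same term for a different list.

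**2. Is there a limit on onset or attribution?** No time window is given. The list expressly covers events that may be due to airway management, so attribution does not remove an event from it.

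**3. Does expedited notice catch it?** The trigger needs three conditions together: serious, unexpected and possibly related. An arrest classed as expected fails the second, even if the site thinks the device caused it.

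**4. Where does each kind of arrest appear?** The interim composite in 2.6.6 is mortality, failure to place the airway on the first attempt, or failure to ventilate. The timed 24-hour list under Other Adverse Events in 2.5 covers airway trauma, pneumothorax, aspiration pneumonitis, ARDS and ventilator-associated pneumonia.

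| Arrest around the airway attempt | Interim composite | Timed 24-hour list | Identified as an arrest |
|---|---|---|---|
| Fatal | Yes, as a death | No | No |
| Survived, first attempt failed | Yes, as a failed attempt | No | No |
| Survived, placed first time, ventilation failure recorded | Yes, as failure to ventilate | No | No |
| Survived, placed first time, no ventilation failure recorded | No | No | No |

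The last row is the gap.

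**5. Do the sections agree?** Section 2.6.6 promises serious adverse events by group, with frequency, description and date, and does not restrict them to unexpected events. Section 6.3.1 sends the DSMB no expected events. The documents do not say which prevails. If the term in 2.5 is carried into 6.3.1, airway trauma and pneumothorax would also go unreported to the DSMB as adverse events.

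**6. How many subjects are exposed?** Inputs: 287 subjects per period, seven periods, six steps (2.1.1); interim analyses after periods 3 and 5 of 2,009 subjects (2.6.6).

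- The plan's own figures first: 287 × 3 = 861 and 861/2,009 = 42.9% (stated 43%); 287 × 5 = 1,435 and 1,435/2,009 = 71.4% (stated 71%).
- With equal enrollment per step group, SGA subjects through period k = 287 × [0 + 1 + … + (k − 1)]/6.
- k = 3: 287 × 3/6 = 143.5, about 144.
- k = 5: 287 × 10/6 = 478.3, about 478.
- k = 7: 287 × 21/6 = 1,004.5, about 1,005.

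Equal enrollment is an assumption. Seventeen agencies over six steps is 17/6 = 2.83 per step, so the groups cannot contain equal numbers of agencies.

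**The case against.** A reader might infer that an arrest at insertion reaches nobody. The documents do not support that. Fatal arrests count in 24-hour mortality and in the composite compared by group, and arrests with a failed first attempt or failure to ventilate also enter the composite. Sites document potential adverse events (6.3), and procedure complications and transport vital signs are abstracted (2.6.9). The DSMB reviews collected data (6.2.1), its chairperson can call an emergency meeting (6.1), and unanticipated problems involving risk have their own reporting column (6.3.1). All of this stands and confines the gap to the last row of the table above. These routes are aggregate, delayed or a matter of judgement, and none requires an individual report of that arrest. Unanticipated-problem reporting fits poorly with an event already called expected, and for the FDA, Department of Defense and DSMB it waits on an IRB determination.

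A reader might also take it as stated that an event's name alone makes it expected. That is inference. The classification step in 6.3 could be read as a case-by-case judgement, and 2.6.6 could be read as overriding the table. This supports reconciling the text and does not show that the gap is closed. Section 2.6.6 leaves the final monitoring plan to be developed with the DSMB, and 6.1 leaves serious event procedures to its first meeting, so the matter may be settled there.

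Some exemption is reasonable. Patients with return of circulation are eligible and form a predefined subgroup (2.6.3), so re-arrest from injury is foreseeable in both arms. That argues for a narrower exemption with aggregate counts, and against reporting every arrest on an expedited clock.

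**Conclusion.** The concern holds in this limited form. On the natural reading of 6.3 and 6.3.1, a survived arrest around the airway attempt, with successful first placement and no recorded ventilation failure, need not be reported individually. It falls outside both the interim composite and the timed event list. Other arrests around the attempt are counted, but only as deaths, failed attempts or failures to ventilate. The exemption applies equally to both arms.

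The conclusion rests on reading the listed events as the expected ones, which is natural but not explicit. The conflict between 2.6.6 and 6.3.1, and the second use of the term in 2.5, stand on either reading.

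The documents give no arrest rate, so neither the number of affected events nor any excess can be estimated. The only available measure of size is exposure: about 144, 478 and 1,005 SGA subjects at the two interim analyses and the end, if enrollment is equal across the six step groups. The text should be changed, because the gain in safety monitoring is specific and the cost is low.

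**What to change.** 1. Reconcile Sections 2.5, 2.6.6, 6.3 and 6.3.1: give one definition of an expected adverse event, and state whether the serious adverse events promised to the DSMB include expected ones.
2. In 6.3, delete the catch-all at the end of the list.
3. In 6.3, do not apply the exemption to any listed event, cardiac arrest included, with onset between the start of the first advanced airway attempt and transfer of care at the trauma center. Record these as adverse events and assess them for relatedness, in both arms.
4. In the 6.3.1 table, replace the DSMB entry for expected events with aggregate counts by arm and period at each scheduled review. Period is needed because SGA exposure rises with calendar time in this design.

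Transfer of care is a judgement about where to draw the line. Section 2.5 follows airway conversion for 24 hours, and a later arrest during conversion would appear only in the counts under item 4.

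The cost is protocol wording and one DSMB table. There would be more adverse event forms, and some arrests due to injury would be reported. Section 2.6.9 names procedure complications and vital signs but not arrest, and 6.3 makes recording of the listed events optional, so a dedicated field for arrest and its time may be needed. Treatment is unchanged.

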6.3.1 Adverse Events Reporting Timeline

A table summarizing reporting timelines is provided below:

Organization	Fatal/Life Threatening Reportable Adverse Event	Non-fatal, non-life threatening Reportable Adverse Event	Expected Adverse Events	Unanticipated Problem (not involving risk)	Unanticipated Problem (involving risk)
IRB	24 hours	10 working days	No requirement	No requirement	10 working days
FDA	7 calendar days	15 calendar days	No requirement	No requirement	14 days*
Dept of Defense	7 calendar days	No requirement	No requirement	No requirement	14 days*
DSMB	24 hours	7 calendar days	No reporting	At next meeting (every 6 months)	14 days*

*Reporting occurs only after an IRB determination of UPIRTSO has been received

6.4 RISKS MANAGEMENT PROCEDURES

6.4.1 Protection Against Risks of Data Collection

The collection of sensitive information about subjects is limited to the amount necessary to achieve the aims of the research, so that no unneeded sensitive information is being collected. All

demographic and clinical information about the subject will be stored in an electronic password protected electronic data management system under the supervision of the DCC for this protocol. All staff involved in this study will be properly credentialed and instructed in the areas of testing, confidentiality, and safety.

The Investigator will retain the data for the entire period of this study and will retain the specified records and may continue to use and disclose subjects' de-identified information for the purpose of this study for a minimum of seven years after final reporting or publication of the study. If the subject is a minor, records will be retained until his/her age of majority (18 years) and then for seven years, at minimum. Subject names or other directly identifiable information will not appear on any reports, publications, or other disclosures of clinical study outcomes.

6.5.2 Protection Against Potential Risks of Experimental Intervention

The investigational devices utilized for this trial are those which are already in use by the prehospital providers. All providers have been trained in the proper use of the devices and demonstrate competency in accordance with their local protocols and regulations.

